Across all three studies, we found that patients who used MDTs had higher unplanned hospital use than matched controls, even after regression adjustment (Table 4). Our evaluations estimated that A&E attendances were, on average, between 26% and 40% higher for each of the interventions, and similarly emergency admissions were between 27% and 43% higher. Consistent increases in hospital activity were also observed across type of emergency admission – for chronic ambulatory care sensitive (chronic ACS) or urgent care sensitive (UCS) conditions – and for emergency bed days in Fylde Coast and emergency length of stay in NEHF. In other words, we consistently found that MDTs appeared to increase unplanned hospital use in these three programmes, contrary to the strategic objectives motivating their design. These results are consistent with other independent evaluations.^{1,2,4,25,26,27} The research questions in this pooled analysis arose from this finding.

| | Table | 1: MDT | programmes | reviewed | in | the | pooled | analysi | s |
|--|-------|--------|------------|----------|----|-----|--------|---------|---|
|--|-------|--------|------------|----------|----|-----|--------|---------|---|

| Multidisciplinary teams – intervention design | Fylde Coast Extensive Care Service (ECS) | Fylde Coast Enhanced Primary Care (EPC) | NEHF Integrated Care Teams (ICT) |
|---|--|---|--|
| Relationship to primary care | Replaces usual GP ('carve-out' from usual primary care) | 'Wrap-around' providing additional coordination and services to usual GP care | |
| Implementation start date | August 2015 | November 2016 | July 2015 |
| Implementation and team structure | 10 ECS teams were mobilised, across six hubs. 2 care hubs were launched with the service in June 2015, 2 more opened in May 2016, and the final 2 started in October 2016. | 8 EPC teams were fully mobilised across the Fylde Coast vanguard area by February 2017, and largely overlapped with the ECS care hubs. | 5 ICTs, 1 in each of NEHF's 5 localities, Farnborough, Farnham, Yateley, Fleet and Aldershot, were introduced in July 2015. |

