| Emergency admissions [*] | 27% higher (15% to 41% higher) | 42% higher (29% to 56% higher) | 43% higher (23% to 67% higher) |
| Chronic ACS emergency admissions [*] | 62% higher (33% to 98% higher) | 32% higher (4% to 66% higher) | 105% higher (32% to 222% higher) |
| UCS emergency admissions* | 24% higher (3% to 48% higher) | 46% higher (21% to 75% higher) | 76% higher (35% to 129% higher) |
| Average length of emergency stay, nights [*] | N/A | N/A | 33% higher (8% to 63% higher) |
| Emergency hospital bed days | 8% higher (9% lower to 28% higher) | 57% higher (31% to 88% higher) | N/A |
| Emergency readmissions within 30 days of discharge | N/A | N/A | 4% higher (11% lower to 21% higher) |
| Elective admissions (ordinary or non-regular day admissions) | 8% higher (5% lower to 24% higher) | 2% lower (14% lower to 10% higher) | 24% lower (2% to 41% lower) |
| Elective bed days | 1% higher (34% lower to 54% higher) | 18% lower (25% to 10% lower) | N/A |
| Outpatient attendances | 10% higher (4% to 17% higher) | 11% higher (5% to 16% higher) | 3% higher (8% lower to 17% higher) |
| Deaths in hospital | 43% higher (2% to 100% higher) | 21% higher (12% lower to 67% higher) | 27% lower (42% lower to 2% higher) |
| Deaths [*] (placebo test) | 4% higher (16% lower to 28% higher) | 58% higher (33% to 89% higher) | 22% higher (12% lower to 68% higher) |

Note: all relative differences are rate ratios, apart from deaths and deaths in hospital, which are odds ratios.

Outcomes proposed for the pooled analysis.

*

18

Potential causes of increased emergency hospital use for patients enrolled in MDTs

There are several plausible hypotheses consistent with the results we observed and previous research^{1,10}:

- H1 Residual unobserved confounding (differences in eg social context, end of life)
- H2 Patient-specific effects (subgroup heterogeneity)
- H3 Limited 'impactability' of riskiest patients
- H4 Delayed impact caused by patient and/or provider factors
- H5 Induced demand from clinical risk aversion
- H6 Hospital use does not adequately measure quality.

H1. Residual unobserved confounding accounts for impacts, as MDT patients were still different from their matched controls in unseen but important ways

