The overall outcomes underpinning this study relate to emergency hospital use, as this analysis aims to understand why patients enrolled in MDTs have in general higher emergency hospital use than their comparison groups. While these measures are not the only informative outcomes for assessing the value and impact of integrated care, national and local health and care commissioners in the UK set out to reduce unplanned hospital use by establishing these MDTs in the community, to complement and in some cases replace routine primary care. Measures of unplanned hospital use are conventionally used to summarise the health services impact of interventions, particularly in England.^{54,55} Using common outcome measures allows for more straightforward comparison between different studies.

The primary outcomes to be examined are:

- rate of A&E attendances
- rate of emergency (non-elective) hospital admissions
- average emergency admission associated length of stay (LoS)
- rate of chronic ambulatory care sensitive (chronic ACS) emergency admissions
- rate of urgent care sensitive (UCS, also known as acute ACS or AACS) emergency admissions.

We will also examine:

rate of deaths (independent of whether they occurred in and outside of hospital), as
a diagnostic check. We use mortality rate as a 'placebo test', 'falsification', or 'negative
control' for potential unobserved confounding, ie to check that the treatment and
counterfactual groups are similar at baseline, as mortality risk may be a proxy for severity
of disease. We typically do not expect relatively short exposures to MDTs to materially
impact life expectancy. Prior evidence about MDTs and mortality is weak; based on
previous programme theory and evaluation, it may be the case that improved quality of
care through MDTs can delay death. Given the safety profile of MDT health coaching and
interventions to coordinate communication and care referrals, we would not expect that
MDTs plausibly increase deaths.

Patient subgroups

These analyses will be carried out for the overall population of MDT-treated patients and the counterfactual, alongside up to seven subgroup analyses to assess patient-level heterogeneity. These subgroups are pre-specified below on the basis of past research on MDTs and English policies that have identified these groups as suitable for community case management.⁸

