In NEHF, potential controls (consisting of individuals registered with a GP in NEHF) were only defined by age across the study sample, irrespective of locality (the equivalent to Fylde neighbourhoods). Thus, the youngest control individual retained for analysis was at most 2 years younger than the youngest overall NEHF patient (irrespective of gender), with this rule applied symmetrically for maximum ages.

For the planned analyses, the criteria for 'slimming' potential donor controls by age has been adapted for consistency across the three studies: control pools are pre-specified to be 2 years around the minimum and maximum ages of all MDT intervention patients, by gender, in the respective MDT studies.

Exploratory data analyses on heterogeneity, on stacked original analysis data (using matched controls)

First, we will 'stack' or directly combine the three original matched data sets, according to a commonly mapped variable list that has been pre-defined (Table 5). Variable names and definitions are largely but not entirely consistent between the three IAU evaluations. Some will be adjusted so that both our stacked matched data set and our pooled data set have consistent definitions, variables and outcomes across all three studies. For example, for Fylde we will calculate emergency admission-associated length of stay, while the original analysis looked at emergency hospital bed days. Similarly, some of the flags used for risk adjustment will change, including removing some historic hospital activity and updated definitions for mental ill health flags in Fylde (see Table 5). In this initial phase, the individual intervention and matched control patients, as well as follow-up period, will be exactly the same units as those included in the original evaluations.

We will also add a set of new variables that capture social context characteristics, which aim to improve the similarity between the intervention group and their counterfactual. These are discussed in the next section.

Table 5. Potential baseline variables for regression on stacked data sets and for entropy balancing on pooled data

| V | ariables at patient level | Changes to the original individual study analyses | | | | | | | | | | | | | | | | | | | | | | | | | | | | | | | | |
|--------|---|---|--|---|--|--|---|---|--|---|---|--|--|---|---|---|---|--|---|--|---|--|---|---|---|--|---|---|---|---|--|--|---|--|

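### Emergency bed days are dropped and average length of stay is pooled as a primary outcome; it depends on post-enrolment admission and can fall while total days in hospital do not.

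*SAP*

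**What the plan says.** The Study endpoints section of the SAP lists five primary outcomes. Two matter here: "rate of emergency (non-elective) hospital admissions" and "average emergency admission associated length of stay (LoS". Emergency bed days are not in the list. In Table 4 the bed-days row lacks the asterisk that marks outcomes proposed for the pooled analysis, while the length-of-stay row has it.

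The section on exploratory analyses of the stacked data gives the reason, which is consistent definitions across the three studies: "for Fylde we will calculate emergency admission-associated length of stay, while the original analysis looked at emergency hospital bed days". NEHF had already reported length of stay and not bed days, so only Fylde (ECS and EPC) changes. Table 5 makes a matching change at baseline: emergency bed days in year -1 are removed in both areas, and average emergency stay in year -1 is a listed covariate.

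On the original results, the SAP says that "we consistently found that MDTs appeared to increase unplanned hospital use in these three programmes". It keeps residual confounding (H1) and induced demand (H5) open as explanations. It does not say how average stay is defined for a patient with no emergency admission.

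**The concern.** Entropy balancing makes all enrolled patients and the weighted controls alike on pre-enrolment characteristics. It does not do this for the subset of each group that is later admitted. Average stay is informative only about that subset, and the rate of entering it differed between groups in every original study. The contrast in average stay is therefore not the average treatment effect on the treated that the SAP sets out to estimate. This holds whether the extra admissions come from the MDT or from unmeasured severity.

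There is also a mechanical problem. If the additional admissions are shorter than usual, the average falls while days in hospital rise. A reader could then take a shorter stay for a benefit. The SAP's own background invites this: under H2 it counts shorter stay among measures of reduced hospital use, and under H6 it describes shortening stay as the usual aim at end of life, which is one of the planned subgroups.

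**Working it through.** **Inputs (SAP, Table 4, rate ratios with 95% CI).**

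| | ECS | EPC | NEHF ICT |
|---|---|---|---|
| Emergency admissions | 1.27 (1.15–1.41) | 1.42 (1.29–1.56) | 1.43 (1.23–1.67) |
| Emergency bed days | 1.08 (0.91–1.28) | 1.57 (1.31–1.88) | not reported |
| Average emergency stay | not reported | not reported | 1.33 (1.08–1.63) |

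**Step 1: the plan's own figure.** The SAP text gives emergency admissions as 27% to 43% higher. Table 4 gives 27%, 42% and 43%, so the range is reproduced. The geometric mid-points of the three intervals are 1.273, 1.419 and 1.433, so the estimates and intervals agree.

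**Step 2: implied stay per admission.** If average stay is total bed days over total admissions, its ratio is the bed-day ratio divided by the admission ratio.
- ECS: 1.08/1.27 = 0.85, about 15% shorter.
- EPC: 1.57/1.42 = 1.11, about 11% longer.
- NEHF: 1.33 as reported. Implied bed days are 1.43 × 1.33 = 1.90.

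**Step 3: uncertainty.** SE of each log ratio = ln(upper/lower)/(2 × 1.96). For ECS, bed days give ln(1.28/0.91)/3.92 = 0.087 and admissions give ln(1.41/1.15)/3.92 = 0.052. The SE of the difference is √(0.087² + 0.052² − 2ρ × 0.087 × 0.052). The correlation ρ is not in the SAP, so a range is assumed.

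| ρ | ECS implied stay 0.85 | EPC implied stay 1.11 |
|---|---|---|
| 0 | 0.70–1.04 | 0.90–1.36 |
| 0.5 | 0.73–0.99 | 0.95–1.29 |
| 0.8 | 0.76–0.95 | 0.98–1.25 |

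**Step 4: mechanism.** Suppose the extra admissions last f times the usual stay and other stays are unchanged. With admission ratio RR, the bed-day ratio is 1 + (RR − 1)f and the stay ratio is [1 + (RR − 1)f]/RR. For any RR above 1 and f between 0 and 1, bed days rise and average stay falls. At RR = 1.27 and f = 0.30, bed days are 1 + 0.27 × 0.30 = 1.08 and stay is 1.08/1.27 = 0.85, which are the ECS figures. For EPC the same model needs f = 0.57/0.42 = 1.36, meaning extra stays longer than usual, so the mechanism does not describe EPC.

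**Step 5: pooled direction.** Inverse-variance pooling of 0.85, 1.11 and 1.33 gives a fixed-effect ratio from 1.07 (0.95–1.21) at ρ = 0 to 1.00 (0.93–1.08) at ρ = 0.8. The random-effects ratio lies between 1.06 and 1.08, and its intervals also include 1.

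**Step 6: the consistency check.** The SAP will validate entropy balancing by asking for estimates within 15% of the earlier ones. For length of stay, Table 4 has no earlier Fylde estimate. Fylde supplies 1,626 + 3,011 = 4,637 of 5,411 MDT patients (86%). Bed days have an earlier estimate in both Fylde studies.

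**The case against.** The strongest reply is that the rise in admissions is not hidden. The emergency admission rate stays a primary outcome beside length of stay, and the two together give approximate bed days, as Step 2 does for NEHF. Length of stay also has a rationale: it was already an NEHF outcome, the SAP cites reviews that report it, and common measures ease comparison. This stands, and it is why length of stay need not be removed or demoted. It does not make average stay a comparison of balanced groups. A reader of a subgroup result would still have to work out whether total days rose or fell, without an interval.

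A reader might infer that extra short admissions will make MDTs look beneficial. The documents do not support that: only ECS implies a shorter stay, EPC and NEHF point to longer ones, and the pooled value sits near or above 1. A reader might also infer that ECS has been shown to change sign. Its bed-day interval runs from 9% lower to 28% higher, and the implied stay ratio excludes 1 only under the stronger assumed correlations. Nor do the documents establish that MDTs caused the admissions, since H1 remains open.

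The baseline change in Table 5 is minor. Year -1 emergency admission counts remain in the list, and baseline stay involves no post-enrolment selection.

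**Conclusion.** The point holds in a limited form. The plan omits the measure of total emergency days and pools one that is conditional on an event 27% to 43% more frequent in MDT patients. In one of the three studies the SAP's own figures imply that the two measures point in opposite directions: ECS stay about 0.85 against bed days 1.08. The other two do not show this, so the direction of bias in the pooled length of stay cannot be stated in advance.

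The 0.85 and 1.11 are approximations. They divide separately modelled adjusted ratios, and they assume that average stay behaves as total days over total admissions; a patient-level average may differ. Their intervals depend on an assumed correlation. The conditioning problem itself rests only on reading average stay as a per-admission measure, which its name implies. If patients never admitted were coded as zero, the outcome would no longer be a length of stay, and the SAP should say so.

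**What to change.** In Study endpoints and in the section on the stacked data, add emergency bed days per person-time at risk, with zero for patients never admitted, as a harmonised outcome in all three studies alongside length of stay. Use bed days for the consistency check against the earlier Fylde estimates. State how average stay is defined for patients with no emergency admission, that it is conditional on admission, and that it is not to be read alone as an MDT effect. Preferably keep year -1 emergency bed days as a baseline covariate in Table 5; that table lists it as removed for NEHF, so it has been derived there before.

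The cost is SAP wording, one NEHF outcome to compute from hospital data already held, a more skewed outcome to model, and one more outcome to report.

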There are several plausible hypotheses consistent with the increased emergency hospital use we observed in the original studies, as well as in previous research.^{10,11}

- H1 Residual unobserved confounding: although the control groups were similar to the intervention groups on observable characteristics, there may have been unobserved differences between the intervention and control groups which affected the outcomes.
- **H2 Patient-specific effects:** MDTs may be best suited to support certain patient subgroups, for instance with particular long-term conditions.
- **H3** Limited 'impactability' of riskiest patients: there may be limited scope to reduce emergency hospital use for those identified as being at the highest risk, especially if they are nearing their end of life.
- **H4 Delayed impact:** MDTs increase hospitalisation initially but sustain eventual reductions in hospital use after an initial delay caused by patient and/or provider factors (eg identifying unmet need in the short term and/or time needed to embed complex change).
- **H5 Induced demand:** MDTs may have led to patients being more aware of their health needs or risks or health professions being risk averse, which in turn led to greater hospital and other service use.
- **H6** Measuring hospital use does not adequately reflect quality: the value of integrated care teams may primarily lie in measures other than reducing emergency hospital admissions.

We will explore some of these hypotheses.

Firstly, the IAU seeks to further explore the potential impact of **unobserved confounding** as an explanation for the increase in hospital use associated with MDTs in the original evaluations. We will try to improve the level of similarity between the referred and matched control groups by exploring characteristics related to 'social context', some of which may be proxies for social isolation. These are: living alone, recently started to live alone, living with somebody with certain LTCs, a recent bereavement within the household or frequent moves in the last year. Stokes et al found that, when identifying patients for MDTs, medical practitioners felt that the patients' needs were often primarily related to social factors such as isolation, poor housing or living arrangements and other socio-economic issues.² Factors such as living alone have been found to be associated with emergency hospital use.¹²

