| Social context Living alone Living with somebody with dementia or frailty[†] Recently living alone (change in last X months)[†] Bereavement in last X months[†] Number of moves in last 12 months | New variables to be refined and added as a key output of the pooled analysis – ATT estimated effects from the previous evaluations may or may not be robust to inclusion of such social context factors when identifying and matching/weighting for potential controls. If ATTs are not robust, the analysis will demonstrate clear evidence of previously unobserved confounding | |

Note: these are potential covariates and may not all have been included in both the matching and regression stages in the original studies (see technical reports for further details).

* Health variables are identified from hospital records in the 3-year pre-period.

t Exploratory analysis will establish exact definition (see section on social context).

The Elixhauser and Charlson lists of comorbidities are routinely used for risk adjustment.^{57,58,60,66} The Elixhauser list is broader than the Charlson list and consists of the following 30 comorbidities: congestive heart failure; chronic pulmonary disease; hemiplegia or paraplegia; metastatic solid tumour or metastatic cancer; acquired immune deficiency syndrome or human immunodeficiency virus; peripheral vascular disease; cardiac arrhythmias; valvular disease; pulmonary circulation disorders; hypertension (uncomplicated); hypertension (complicated); other neurological disorders; diabetes (uncomplicated); diabetes (complicated); hypothyroidism; renal failure; liver disease; peptic ulcer disease (excluding bleeding); lymphoma; solid tumour without metastasis, rheumatoid arthritis or collagen vascular diseases; coagulopathy; obesity; weight loss; fluid and electrolyte disorders; blood loss anaemia; deficiency anaemia; alcohol abuse; drug abuse; psychoses; depression.^{57,58} Most of the comorbidities on the Charlson list are covered by the Elixhauser list.^{58,60,66} One notable exception is dementia; therefore, dementia is included separately (see Table 5).

The following list of comorbidities is considered linked to frailty: anxiety or depression; functional dependence; falls and significant fracture; incontinence; mobility problems; pressure ulcers; and cognitive impairment (composite of delirium, dementia and senility), consistent with other IAU analyses.^{59,67}

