- 1. Living alone flag. This variable shows whether a person was living alone at baseline (start date, or index date). For intervention patients, this will be their status in the month prior to being enrolled in an MDT. For potential controls, this will be calculated monthly, for each of the monthly index dates that were assigned, between the start of the study period and 1 month before the end of the study period (which was the last date a patient could join the study, as per the original studies, to ensure at least 1 month of follow-up).
- Living with somebody who has pre-specified long-term conditions (dementia or 2. frailty, to be determined). This variable captures whether a person, at baseline, is living with somebody who has at least one pre-specified condition. We will investigate dementia and a broader group of indicators of frailty (including dementia) as two potential conditions or characteristics that may lead to social isolation for a carer if they do not feel able to leave the person at home on their own or have difficulty in managing their own conditions or accessing the care they need. Other potential variables which were discarded due to likely small sample sizes in our data were serious mental ill health and paralysis. As in the original analyses, conditions are identified from the patient's hospital SUS records in the 3 years prior to the index date, using the same definitions as for patients' baseline characteristics. For dementia, we will use the definition used in the Charlson index;^{58,60,66} for frailty, we will use the Soong definition.⁵⁹ The 'living with somebody with dementia/frailty' flag will not apply to individuals living in care homes or at addresses where seven or more people are registered. This is because larger numbers could be indicative of other living establishments, eg prison. According to the Office for National Statistics, approximately 2% of households in the UK contain six or more people³¹ therefore setting the threshold at seven will exclude only a very small percentage of households (<2%).
- 3. **Recent change to living alone.** This variable will capture the household shrinking from two or more people to one person, within a specific period (lookback period to be determined). This shrinkage could be as a result of bereavement, divorce, partner moving to a care home or a single parent's child moving out.

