- 4. **Bereavement.** Any bereavement within a household, independent of number of people left in the household within a specific period (lookback period to be determined). This variable will not apply to individuals living in care homes or at addresses where seven or more people are registered.
- 5. **Change: Multiple moves in last 12 months.** This is where a person changed address at least twice, as identified as having had three or more different pseudo-UPRNs, within 12 months.

For bereavement and recent change to living alone, before determining the lookback period we will first explore the time period that best characterises the patients that were enrolled in MDTs, ie affected treatment assignment. We will explore 3 and 12 months' lookback. Based on baseline characteristics, we will also determine whether to look at dementia or frailty for other household members.

We will start by examining whether there are differences in the social context variables at baseline between the original intervention and matched control patients, in each of the three studies individually. For those variables that look promising, we will quantify their effect on the outcomes for the original intervention and matched control groups, by including these social context variables in a subsequent outcome regression.

We may also explore five or fewer pre-specified two-way interaction effects, eg:

- recent bereavement with living alone
- mental ill health with bereavement
- mental ill health with recently living alone.

If these variables are shown to be important to adjust for we will include them in the entropy balancing and subsequent analyses, as appropriate.

We will also create a flag for whether the person died within 90 days of being enrolled in an MDT or being selected as a control, as a proxy for nearing their end of life. We will check for any imbalances between intervention and matched controls in this variable, which may suggest previously unobserved differences in disease severity or frailty that may confound emergency hospital admission rates. We will also check for any imbalances between intervention patients in the three studies, which would indicate heterogeneity.

We will create subgroups based on this EOL flag and check the balance between the intervention and matched control groups on patient characteristics.

Handling of differential information from risk scores

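### The multiple-moves flag requires three different addresses, so people who move away and come back are coded as not having moved repeatedly

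*SAP*

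**What the plan says.** The social context indicators are defined in the SAP under 'Exploratory data analyses: improving on unobserved confounding by exploring social context factors and a proxy for end of life'.

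- **Indicator 5 (multiple moves)** applies to a person who "changed address at least twice, as identified as having had three or more different pseudo-UPRNs, within 12 months". Table 5 lists the corresponding covariate as "Number of moves in last 12 months". It does not carry the dagger that leaves the exact definition of three other social context variables to exploratory work.
- **Indicator 3 (recent change to living alone)** reads: "This variable will capture the household shrinking from two or more people to one person". Its examples are: "This shrinkage could be as a result of bereavement, divorce, partner moving to a care home or a single parent's child moving out". The section 'What the study will look at' describes the intended factors as including "living alone, recently started to live alone, living with somebody with certain LTCs".
- **Indicator 4 (bereavement)** covers: "Any bereavement within a household, independent of number of people left in the household".

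In Table 5 the dagger is on both recently living alone and bereavement. The only open item the text names for these two is the lookback, with 3 and 12 months to be explored. 'Sources of data' says household status comes from comparing pseudo-UPRNs between persons. Indicators found important to adjust for go into the entropy balancing and later analyses.

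**The concern.** For indicator 5 the SAP states a concept, two or more changes of address, and then a rule meant to identify it, three or more distinct addresses. If the two differ, the flag is wrong for some people by the SAP's own definition. The discussion of H1 names housing instability as a possible reason for referral, and moving out and back is one form of it.

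The flags also decide what happens next. Only variables that look promising at baseline are taken into the outcome regression, and the counterfactual is rebuilt with them only if balance was poor and they may affect outcomes. A flag that misses cases can understate an imbalance at that stage, and adjusting for it removes less of whatever confounding exists.

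**Working it through.** **Inputs.** The concept, rule and 12-month window are from indicator 5, and the covariate description is from Table 5. The share *r* of people with exactly two changes who return to their first address is not in the SAP. It is assumed here to lie between 5% and 50%, for illustration only.

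**Step 1: does the rule equal the concept?** Let *k* be the number of changes of address and *d* the number of distinct addresses. Since *d* ≤ *k* + 1, *d* ≥ 3 implies *k* ≥ 2, so the rule never flags anyone below the stated concept. The converse fails, because a history with *k* ≥ 2 can use only two addresses. Listing every pattern in which consecutive addresses differ:

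| Changes *k* | Possible patterns | Meets concept (*k* ≥ 2) | Missed by rule (*d* < 3) |
|---|---|---|---|
| 0 | 1 | no | – |
| 1 | 1 | no | – |
| 2 | 2 (A-B-A, A-B-C) | yes | A-B-A |
| 3 | 5 | yes | A-B-A-B |
| 4 | 15 | yes | A-B-A-B-A |

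The stated equivalence is not reproduced: the rule is sufficient but not necessary. At each *k* ≥ 2 the one missed pattern is alternation between two addresses. These are counts of patterns, not of people.

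**Step 2: sensitivity among people with exactly two changes.** Sensitivity = 1 − *r*.

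- *r* = 5%: 1 − 0.05 = 95%
- *r* = 20%: 1 − 0.20 = 80%
- *r* = 50%: 1 − 0.50 = 50%

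**Step 3: the Table 5 count.** The number of distinct addresses minus one is only a lower bound on the number of moves. For A-B-A it gives 2 − 1 = 1 against 2 moves, and for A-B-A-B it gives 2 − 1 = 1 against 3.

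**Step 4: effect on the baseline comparison.** Let true prevalences of repeat moving be *p*₁ and *p*₀ in the two groups. Suppose sensitivity *s* over all repeat movers is equal in both groups and nobody is falsely flagged. The observed difference is then *s p*₁ − *s p*₀ = *s*(*p*₁ − *p*₀), so any imbalance shrinks by the factor *s*. The SAP does not give *s*, and it is not 1 − *r*, because it also averages over people with more than two changes.

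**Step 5: indicator 3 for a two-person household, under two readings.**

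| Event | Size of the person's own household | Occupancy of the baseline address |
|---|---|---|
| Partner leaves | 2 to 1, flagged | 2 to 1, flagged |
| Partner dies at home | 2 to 1, flagged | 2 to 1, flagged |
| Person moves out to live alone | 2 to 1, flagged | 0 to 1, not flagged |

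The readings differ only for the person who moves out, and the SAP does not say which applies.

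**Step 6: indicator 4.** No arithmetic applies. 'What the study will look at' gives the concept as bereavement inside the household, and the rule counts the same thing. They agree.

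**The case against.** The inequality in indicator 5 cannot be defended on the wording, but several points on the other side carry weight.

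- **Who is missed.** Anyone with three or more addresses in the year is flagged, so it cannot be said that the people with the most unstable housing are lost. The gap also needs the address in GP registration data to change twice within 12 months, and the SAP does not indicate how often that happens for a return move.
- **Noise.** A distinct-address rule resists false switching when an address is re-matched and then reverts. The SAP does not give this as its reason, but the advantage is real.
- **Indicator 3.** A reader might infer that the household flags follow one fixed address, so that people who move out to live alone are coded as unexposed. The SAP does not say so. The flag's title concerns the person, pseudo-UPRNs are held per person, and divorce is listed without saying who leaves. The literal wording only means that such people may be missed, and the definition is still to be settled. Someone who moved out to live alone would in any case be picked up by the separate living-alone flag at baseline.
- **Indicator 4.** A reader might also infer that a spouse whose partner entered a care home and then died is miscoded. That death lies outside the stated concept. Extending it to former co-residents is a preference, not the correction of an error.
- **Inference.** A reader might suppose that the SAP would take an unchanged effect, after adding these flags, as proof against confounding. It does not. It calls the comparison informal, draws a conclusion in Table 5 only where estimates are not robust, and repeats in its limitations that residual differences may remain.

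**Conclusion.** Indicator 5 is wrong as written. People who alternate between two addresses meet its definition and fail its rule, and the rule does not yield the number of moves listed in Table 5. The error runs one way: repeat movers are missed and no one is falsely added, taking the recorded address histories as correct.

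Its size cannot be derived from the SAP. The 50% to 95% range rests on an assumed return share and applies only to people with exactly two changes. Without the prevalence of repeat moving, its imbalance between groups and its association with the outcomes, no statement about remaining bias in the estimated MDT effect is possible.

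For indicator 3 the supportable point is narrower: the SAP should say whose household is compared, and when. No error is shown for indicator 4.

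**What to change.** **Indicator 5.** Replace the distinct-address rule with a count of dated changes of pseudo-UPRN along each person's own address history in the 12 months before the index date. Flag at two or more. This recovers every missed repeat mover, adds nobody with fewer than two recorded changes, and supplies the Table 5 count.

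**Indicator 3.** State in the planned addendum that the flag compares the size of the person's own household at the start of the lookback with its size at baseline, whatever the address.

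**Cost.** A wording change and a different query on address data the SAP already plans to access. Counting changes will admit some spurious ones from address re-matching. Requiring a new pseudo-UPRN to persist over two consecutive extracts would limit these, at the price of missing very short stays. Both choices should be recorded in the addendum before the main analyses.
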